6.3.2. Adverse Events

The investigator or site staff will be responsible for detecting, documenting, and reporting events that meet the definition of an AE or SAE.

6.3.2.1. Definition of an AE

Any untoward medical occurrence in a subject or clinical investigation subject, temporally associated with the use of a medicinal product, whether or not considered related to the medicinal product.

Note: An AE can therefore be any unfavorable and unintended sign (including an abnormal laboratory finding), symptom, or disease (new or exacerbated) temporally associated with the use of a medicinal product. For marketed medicinal products, this also includes failure to produce expected benefits (ie, lack of efficacy), abuse, or misuse.

Events meeting the definition of an AE include:

- Exacerbation of a chronic or intermittent pre-existing condition including either an increase in frequency and/or intensity of the condition
- New conditions detected or diagnosed after study treatment administration even though it may have been present prior to the start of the study

- Signs, symptoms, or the clinical sequelae of a suspected interaction
- Signs, symptoms, or the clinical sequelae of a suspected overdose of either study treatment or a concomitant medication (overdose per se will not be reported as an AE/SAE) unless this is an intentional overdose taken with possible suicidal/self-harming intent. This should be reported regardless of sequelae.

“Lack of efficacy” or “failure of expected pharmacological action” per se will not be reported as an AE or SAE; however, the signs and symptoms and/or clinical sequelae resulting from lack of efficacy will be reported if they fulfill the definition of an AE or SAE.

Events that **do not** meet the definition of an AE include:

- Medical or surgical procedure (eg, endoscopy, appendectomy); the condition that leads to the procedure is an AE
- Situations where an untoward medical occurrence did not occur (social and/or convenience admission to a hospital)
- Anticipated day-to-day fluctuations of pre-existing disease(s) or condition(s) present or detected at the start of the study that do not worsen
- The disease/disorder being studied, or expected progression, signs, or symptoms of the disease/disorder being studied, unless more severe than expected for the subject’s condition

6.3.2.2. Definition of an SAE

An SAE is any untoward medical occurrence that, at any dose:

- a. Results in death
- b. Is life-threatening

NOTE: The term ‘life-threatening’ in the definition of ‘serious’ refers to an event in which the subject was at risk of death at the time of the event. It does not refer to an event, which hypothetically might have caused death, if it were more severe.

- c. Requires hospitalization or prolongation of existing hospitalization

NOTE: In general, hospitalization signifies that the subject has been detained (usually involving at least an overnight stay) at the hospital or emergency ward for observation and/or treatment that would not have been appropriate in the physician’s office or outpatient setting. Complications that occur during hospitalization are AEs. If a complication prolongs hospitalization or fulfills any other serious criteria, the event is serious. When in doubt as to whether “hospitalization” occurred or was necessary, the AE should be considered serious.

Hospitalization for elective treatment of a pre-existing condition that did not worsen from baseline is not considered an AE.

- d. Results in disability/incapacity, or

NOTE: The term disability means a substantial disruption of a person's ability to conduct normal life functions. This definition is not intended to include experiences of relatively minor medical significance such as uncomplicated headache, nausea, vomiting, diarrhea, influenza, and accidental trauma (eg, sprained ankle) which may interfere or prevent everyday life functions but do not constitute a substantial disruption.

- e. Is a congenital anomaly/birth defect
- f. Medical or scientific judgment should be exercised in deciding whether reporting is appropriate in other situations, such as important medical events that may not be immediately life-threatening or result in death or hospitalization but may jeopardize the subject or may require medical or surgical intervention to prevent 1 of the other outcomes listed in the above definition. These should also be considered serious. Examples of such events are invasive or malignant cancers, intensive treatment in an emergency room or at home for allergic bronchospasm, blood dyscrasias, or convulsions that do not result in hospitalization, or development of drug dependency or drug abuse.
- g. All events of possible drug-induced liver injury with hyperbilirubinemia defined as ALT $\geq 3 \times$ ULN **and** bilirubin $\geq 2 \times$ ULN ($>35\%$ direct) (or ALT $\geq 3 \times$ ULN and international normalized ratio [INR] >1.5 , if INR measured) termed 'Hy's Law' events (INR measurement is not required and the threshold value stated will not apply to subjects receiving anticoagulants).

NOTE: bilirubin fractionation is performed if testing is available. If testing is unavailable, record presence of detectable urinary bilirubin on dipstick indicating direct bilirubin elevations and suggesting liver injury. If testing is unavailable and a subject meets the criterion of total bilirubin $\geq 2 \times$ ULN, then the event is still reported as an SAE. If INR is obtained, include values on the SAE form. INR elevations >1.5 suggest severe liver injury.

6.3.2.3. Adverse Events of Special Interest

The medical monitor should be notified of the occurrence of the following AEs of special interest:

- Any opportunistic infections, such as infections caused by organisms that do not cause disease in a person with a healthy immune system, or types of infections that do not commonly occur in someone with a healthy immune system (eg, Pneumocystis pneumonia, cryptococcal meningitis, mycobacterium infections, cytomegalovirus retinitis, systemic candidiasis).
- Serious postinjection systemic reactions: subjects may be withdrawn from investigational product administration at the discretion of the investigator.
- PML: follow any cases of suspected PML as per the algorithm in [Appendix 4](#). Confirmed PML is to be reported as an SAE.
- HBV reactivation (see Section [6.3.10.2](#)).
- Severe mucocutaneous reactions (eg, toxic epidermal necrolysis and Stevens-Johnson syndrome).

- Cytopenias.
- Cardiovascular events (see Section 6.3.4).

All infections and serious postinjection systemic reactions should be monitored closely throughout the study and recorded on the AE/SAE forms as soon as possible. As applicable, the investigator must also complete the respective 'Severe Infections' or 'Postinjection Systemic Reaction' eCRF page.

Refer to Section 4.4.2 and Section 4.4.3 for discontinuation and withdrawal criteria.

6.3.3. Laboratory and Other Safety Assessment Abnormalities Reported as AEs and SAEs

Any abnormal laboratory test results (hematology, clinical chemistry, or urinalysis) or other safety assessments (eg, ECGs, radiological scans, vital signs measurements), including those that worsen from baseline, and felt to be clinically significant in the medical and scientific judgment of the investigator are to be recorded as AEs or SAEs.

However, any clinically significant safety assessments that are associated with the underlying disease, unless judged by the investigator to be more severe than expected for the subject's condition, are **not** to be reported as AEs or SAEs.

6.3.4. Cardiovascular Events

Investigators will be required to fill out event specific data collection tools for the following AEs and SAEs:

- Myocardial infarction/unstable angina
- Congestive heart failure
- Arrhythmias
- Valvulopathy
- Pulmonary hypertension
- Cerebrovascular events/stroke and transient ischemic attack
- Peripheral arterial thrombosis
- Deep venous thrombosis
- Revascularization

This information should be recorded within 1 week of when the AE/SAE(s) are first reported.

6.3.5. Death Events

In addition, all deaths, whether or not they are considered SAEs, will require a specific death data collection tool to be completed. The death data collection tool includes questions regarding cardiovascular (including sudden cardiac death) and noncardiovascular death.

This information should be recorded within 1 week of when the death is first reported.

6.3.6. Pregnancy

Pregnancy information will be collected from the start of study treatment through the follow-up contact. Any pregnancy that occurs during study participation must be reported using a clinical trial pregnancy form. To ensure subject safety, each pregnancy must be reported to Novartis within 24 hours of learning of its occurrence. The pregnancy must be followed up to determine outcome (including premature termination) and status of mother and child. Pregnancy complications and elective terminations for medical reasons must be reported as an AE or SAE. Spontaneous abortions must be reported as an SAE.

Any SAE occurring in association with a pregnancy that is brought to the investigator's attention after the subject has completed the study and is considered by the investigator as possibly related to the study treatment must be promptly reported to Novartis.

In addition, the investigator must attempt to collect pregnancy information on any female partners of male study subjects who become pregnant while the subject is enrolled in the study. Pregnancy information must be reported to Novartis as described above.

6.3.7. Time Period and Frequency of Detecting AEs and SAEs

The investigator or site staff is responsible for detecting, documenting, and reporting events that meet the definition of an AE or SAE.

All AEs will be collected from the start of study treatment through the end of the Core Study Period. SAEs and AEs of special interest will continue to be collected during the Individualized Follow-up Period.

SAEs will be collected over the same time period as stated above for AEs. However, any SAEs assessed **as related** to study participation (eg, study treatment, protocol-mandated procedures, invasive tests, or change in existing therapy) or related to a Novartis concomitant medication, will be recorded from the time a subject consents to participate in the study up to and including any follow-up contact. All SAEs will be reported to Novartis within 24 hours, as indicated in Section 6.3.9.

6.3.8. Method of Detecting AEs and SAEs

Care must be taken not to introduce bias when detecting AEs and SAEs. Open-ended and nonleading verbal questioning of the subject is the preferred method to inquire about AE occurrence. Appropriate questions include the following:

- “How are you feeling?”
- “Have you had any (other) medical problems since your last visit/contact?”
- “Have you taken any new medicines, other than those provided in this study, since your last visit/contact?”

6.3.9. Prompt Reporting of Serious Adverse Events and Other Events to Novartis

Investigators must report all events meeting the protocol-defined criteria for SAEs, pregnancies, and liver function abnormalities to Novartis promptly, as described in [Table 6-4](#), once the investigator determines that the event meets the definition.

Table 6-4 Reporting of Serious Adverse Events and Other Events to Novartis

Type of Event	Initial Reports		Follow-up Information on a Previous Report	
	Time Frame	Documents	Time Frame	Documents
All SAEs	24 hours	"SAE" data collection tool	24 hours	Updated "SAE" data collection tool
Cardiovascular or Death events: Additional information	1 week	"CV events" and/or "Death" data collection tool(s)	1 week	Updated "CV events" and/or "Death" data collection tool(s)
Pregnancy	24 hours	"Pregnancy Notification Form"	2 weeks	"Pregnancy Follow-up Form"
Nonserious adverse events related to study treatment	5 days (calendar)	"Adverse Reaction" data collection tool	2 weeks	Updated "Adverse Reaction" data collection tool
ALT \geq 3 \times ULN and bilirubin \geq 2 \times ULN (>35% direct) (or ALT \geq 3 \times ULN and INR >1.5, if INR measured) ^a	24 hours ^b	"SAE" data collection tool. "Liver Event" Documents (ie, "Liver Event CRF" and "Liver Imaging" and/or "Liver Biopsy" CRFs, if applicable) ^c	24 hours	Updated "SAE" data collection tool. Updated "Liver Event" Documents ^c
ALT \geq 8 \times ULN; ALT \geq 3 \times ULN with hepatitis or rash or \geq 3 \times ULN and <5 \times ULN that persists \geq 4 weeks	24 hours ^b	"Liver Event" Documents ^c	24 hours	Updated "Liver Event" Documents ^c
ALT \geq 5 \times ULN plus bilirubin <2 \times ULN	24 hours ^b	"Liver Event" Documents do not need completing unless elevations persist for 2 weeks or subject cannot be monitored weekly for 2 weeks ^c	24 hours	Updated "Liver Event" Documents, if applicable ^c
ALT \geq 5 \times ULN and bilirubin <2 \times ULN that persists \geq 2 weeks	24 hours ^b	"Liver Event" Documents ^c	24 hours	Updated "Liver Event" Documents ^c
ALT \geq 3 \times ULN and <5 \times ULN and bilirubin <2 \times ULN	24 hours ^b	"Liver Event" Documents do not need completing unless elevations persist for 4 weeks or subject cannot be monitored weekly for 4 weeks ^c	24 hours	Updated "Liver Event" Documents, if applicable ^c

- Abbreviations: ALT=alanine aminotransferase; AST=aspartate aminotransferase; CRF=case report form; CV=cardiovascular; INR=international normalized ratio; SAE=serious adverse event; ULN=upper limit of normal
- INR measurement is not required; if measured, the threshold value stated will not apply to subjects receiving anticoagulants.
 - Novartis must be contacted at onset of liver chemistry elevations to discuss subject safety
 - Liver Event Documents (ie, "Liver Event CRF" and "Liver Imaging CRF" and/or "Liver Biopsy CRF," as applicable) should be completed as soon as possible.

The SPM provides direction regarding the recording, reporting/transmitting, and follow-up of SAEs.

Prompt notification of SAEs by the investigator to Novartis is essential so that legal obligations and ethical responsibilities towards the safety of subjects are met.

Novartis has a legal responsibility to notify both the local regulatory authority and other regulatory agencies about the safety of a product under clinical investigation. Novartis will comply with country-specific regulatory requirements relating to safety reporting to the regulatory authority, IRB/IEC, and investigators.

Investigator safety reports are prepared for suspected unexpected serious adverse reactions according to local regulatory requirements and Novartis policy and are forwarded to investigators as necessary.

An investigator who receives an investigator safety report describing a SAE(s) or other specific safety information (eg, summary or listing of SAEs) from Novartis will file it with the [Investigator's Brochure](#) [Ofatumumab/OMB157/GSK1841157 Investigator's Brochure, 2016] and will notify the IRB/IEC, if appropriate according to local requirements.

6.3.10. Laboratory Assessments

6.3.10.1. Clinical Laboratory Data

All protocol required laboratory assessments listed in [Table 6-5](#) must be performed by the central laboratory (unless otherwise specified). Laboratory assessments must be conducted in accordance with the [REDACTED] investigator manual and Protocol Time and Events Schedule ([Table 6-1](#)). Laboratory requisition forms must be completed and samples must be clearly labeled with the subject number, protocol number, site number, and visit date. Details for the preparation and shipment of samples and reference ranges for all safety parameters will be provided to the site by the central laboratory.

If additional laboratory assessments not specified in the protocol are performed at the institution's local laboratory and result in a change in subject management or are considered clinically significant by the investigator (eg, SAE or AE), the event(s) must be recorded in the subject's case report form (CRF). Refer to the [REDACTED] investigator manual for appropriate processing and handling of samples to avoid duplicate and/or additional blood draws.

Table 6-5 Laboratory Testing

Chemistry	Hematology	Urinalysis	Other
Total protein	Platelet count	Appearance	Hepatitis B: ^b
Albumin	RBC count	Specific gravity	- HBV surface antigen
ALT	Hemoglobin	pH	- HBV surface antibody
AST	Hematocrit	Protein	- anti-HBc
Alkaline phosphatase	WBC count	Glucose	- HBV DNA PCR
Gamma-glutamyl transferase	WBC differential (automated)	Ketones	Hepatitis C antibody ^b
Total bilirubin	- Neutrophils	Leukocyte esterase (leukocytes)	Immunoglobulins IgG, IgA, IgM ^a
Blood urea nitrogen	- Lymphocytes ^a	Hemoglobin (RBCs)	Pneumococcal antibody assay (Streptococcus pneumoniae IgG antibody assay) ^{a,b}
Creatinine	- Monocytes ^a	Microscopy:	Toxoid antibody assay (Tetanus toxoid IgG antibody assay) ^{a,b}
Creatinine clearance (calculated)	- Bands	- RBC/HPF	High sensitivity C-reactive protein ^a
Sodium	- Eosinophils ^a	- WBC/HPF	B-lymphocyte chemokine ^a
Potassium	- Basophils ^a	- Epithelial cells	
Chloride	Nucleated RBCs	- Trichomonas	
Calcium	CD19+ B-lymphocyte counts ^a	- Bacteria	
Bicarbonate	CD3 ^a	- Yeast	
Glucose	CD4 ^a	- Crystals	
	CD8 ^a	- Ammonium urates	
	CD4:CD8 ratio ^a	- Mucous threads	
		- Amorphous sediment	
		- Casts	
		Microalbumin	Human anti-human antibody ^a
		Creatinine	
		Microalbumin: creatinine ratio	

Abbreviations: ALT=alanine aminotransferase; anti-HBc=hepatitis B core antibody; AST=aspartate aminotransferase; [redacted]; BlyS= B-lymphocyte stimulator; [redacted]; HBV=hepatitis B virus; HPF=high powered field; Ig=immunoglobulin; PCR=polymerase chain reaction; RBC=red blood cell; WBC=white blood cell.

- To maintain study blinding, values will not be reported to investigators during the Treatment or Individualized Follow-up Periods. After the Week 60 visit and all Individualized Follow-up visits, the central laboratory (or designee) will provide the laboratory values and notify the investigator whether or not a subject needs to remain in Follow-up.
- Screening and Week 60/early withdrawal only.
- Note:** Refer to the Time and Events Schedule (Table 6-1) and the [redacted] investigator manual for specific timing of individual laboratory assessments. Laboratory reference ranges are provided in Appendix 13.

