11.3. Appendix 3 – Liver Chemistry Stopping and Follow-up Criteria

Liver Chemistry Stopping Criteria – Liver Stopping Event	
ALT – Absolute	ALT ≥8xULN
ALT – Increase	ALT ≥5xULN but <8xULN persists for ≥2 weeks ALT ≥3xULN but <5xULN persists for ≥4 weeks
Bilirubin ^{1,2}	ALT ≥3xULN and bilirubin ≥2xULN (>35% direct bilirubin)
INR ²	ALT ≥3xULN and INR >1.5, if INR measured
Cannot Monitor	ALT ≥5xULN but <8xULN and cannot be monitored weekly for ≥2 weeks ALT ≥3xULN but <5xULN and cannot be monitored weekly for ≥4 weeks
Symptomatic ³	ALT ≥3xULN associated with symptoms (new or worsening) believed to be related to liver injury or hypersensitivity

Required Actions and Follow-up Assessments following ANY Liver Stopping Event	
Actions	Follow-Up Assessments

 • Immediately discontinue study treatment • Report the event to Novartis within 24 hours • Complete the liver event CRF and SAE data collection tool if the event also meets the criteria for an SAE² • Perform liver event follow-up assessments • Monitor the subject until liver chemistries resolve, stabilize, or return to within baseline (see Monitoring below) • Do not restart subject with study treatment unless allowed per protocol and Novartis Medical Governance approval is granted • If restart is not allowed or not granted, permanently discontinue study treatment and may continue subject in the study for any protocol-specified follow-up 	
 • Viral hepatitis serology⁴ • Only in those with underlying chronic hepatitis B at study entry (identified by positive hepatitis B surface antigen) quantitative hepatitis B DNA and hepatitis delta antibody⁵ • Blood sample for pharmacokinetic (PK) analysis, obtained within 6 weeks after last dose⁶ • Serum creatine phosphokinase (CPK) and lactate dehydrogenase (LDH) • Fractionate bilirubin, if total bilirubin ≥2xULN • Obtain complete blood count with differential to assess eosinophilia • Record the appearance or worsening of clinical symptoms of liver injury or hypersensitivity on the AE report form • Record use of concomitant medications on the concomitant medications report form including acetaminophen, herbal remedies, other over the counter medications • Record alcohol use on the liver event alcohol intake CRF

MONITORING:
	

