
For bilirubin or INR criteria:
 
 Repeat liver chemistries (include ALT, AST, alkaline phosphatase, bilirubin) and perform liver event follow-up assessments within 24 hours A specialist or hepatology consultation is recommended Monitor subjects twice weekly until liver chemistries resolve, stabilize, or return to within baseline 
For all other criteria:
 
 Repeat liver chemistries (include ALT, AST, alkaline phosphatase, bilirubin) and perform liver event follow-up assessments within 24 to 72 hours Monitor subjects weekly until liver chemistries resolve, stabilize, or return to within baseline 	
For bilirubin or INR criteria:
 
 Anti-nuclear antibody, anti-smooth muscle antibody, Type 1 anti-liver kidney microsomal antibodies, and quantitative total immunoglobulin G (IgG or gamma globulins). Serum acetaminophen adduct high-performance liquid chromatography assay (quantifies potential acetaminophen contribution to liver injury in subjects with definite or likely acetaminophen use in the preceding week [James, 2009]). 
Note: not required in China
 
 Liver imaging (ultrasound, magnetic resonance, or computerized tomography) and/or liver biopsy to evaluate liver disease; complete Liver Imaging and/or Liver Biopsy CRF forms.

- Serum bilirubin fractionation should be performed if testing is available. If serum bilirubin fractionation is not immediately available, discontinue study treatment for that subject if ALT $\geq 3xULN$ and bilirubin $\geq 2xULN$. Additionally, if serum bilirubin fractionation testing is unavailable, **record presence of detectable urinary bilirubin on dipstick**, indicating direct bilirubin elevations and suggesting liver injury.
- All events of ALT $\geq 3xULN$ and bilirubin $\geq 2xULN$ (>35% direct bilirubin) or ALT $\geq 3xULN$ and INR >1.5, if INR measured which may indicate severe liver injury (possible 'Hy's Law'), **must be reported as an SAE**; INR measurement is not required and the threshold value stated will not apply to subjects receiving anticoagulants.
- New or worsening symptoms believed to be related to liver injury (such as fatigue, nausea, vomiting, right upper quadrant pain or tenderness, or jaundice) or believed to be related to hypersensitivity (such as fever, rash, or eosinophilia).

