- Includes: Hepatitis A IgM antibody; Hepatitis B surface antigen and Hepatitis B Core Antibody (IgM); Hepatitis C RNA; Cytomegalovirus IgM antibody; Epstein-Barr viral capsid antigen IgM antibody (or if unavailable, obtain heterophile antibody or monospot testing); Hepatitis E IgM antibody.
- If hepatitis delta antibody assay cannot be performed, it can be replaced with a PCR of hepatitis D RNA virus (where needed) [Le Gal, 2005].
- PK sample may not be required for subjects known to be receiving placebo. Record the date/time of the PK blood sample draw and the date/time of the last dose of study treatment prior to blood sample draw on the CRF. If the date or time of the last dose is unclear, provide the subject's best approximation. If the date/time of the last dose cannot be approximated OR a PK sample cannot be collected in the time period indicated above, do not obtain a PK sample. Instructions for sample handling and shipping are in the SPM.

Liver Chemistry Increased Monitoring Criteria with Continued Therapy – Liver Monitoring Event	
Criteria	Actions

ALT \geq5xULN and <8xULN and bilirubin <2xULN without symptoms believed to be related to liver injury or hypersensitivity, and who can be monitored weekly for 2 weeks.
 
OR
 
ALT \geq3xULN and <5xULN and bilirubin <2xULN without symptoms believed to be related to liver injury or hypersensitivity, and who can be monitored weekly for 4 weeks.
	
 • Notify the Novartis medical monitor within 24 hours of learning of the abnormality to discuss subject safety. • Subject can continue study treatment. • Subject must return weekly for repeat liver chemistries (ALT, AST, alkaline phosphatase, bilirubin) until they resolve, stabilize, or return to within baseline. • If at any time subject meets the liver chemistry stopping criteria, proceed as described above. • If ALT decreases from ALT \geq5xULN and <8xULN to \geq3xULN but <5xULN, continue to monitor liver chemistries weekly. • If, after 4 weeks of monitoring, ALT <3xULN and bilirubin <2xULN, monitor subjects twice monthly until liver chemistries normalize or return to within baseline.

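### Eosinophil results are masked with no liver exception, so at ALT ≥3 to <8×ULN an investigator may continue dosing without seeing a sign the liver stopping rule names

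*Protocol*

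**What the plan says.** **Masking.** In Protocol Section 6.3.10.1, Table 6-5 lists "Eosinophils ^a" in the white-cell differential. Footnote a reads: "To maintain study blinding, values will not be reported to investigators during the Treatment or Individualized Follow-up Periods". Lymphocytes, monocytes and basophils carry the same mark; white-cell count, neutrophils and bands do not. The footnote provides for release of values after Week 60, but the last dose is at Week 56.

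**Stopping rule.** Appendix 3 makes ALT ≥3×ULN a stopping event when it is "associated with symptoms (new or worsening) believed to be related to liver injury or hypersensitivity". Its note 3 explains that this includes symptoms "believed to be related to hypersensitivity (such as fever, rash, or eosinophilia").

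**Continue-treatment branch.** Subjects with ALT ≥3 to <5×ULN or ≥5 to <8×ULN and bilirubin <2×ULN may stay on treatment if weekly monitoring is possible and they are free of such symptoms. The upper band is worded "without symptoms believed to be related to liver injury or hypersensitivity, and who can be monitored weekly for 2 weeks". The actions are "Notify the Novartis medical monitor within 24 hours of learning of the abnormality to discuss subject safety" and "Subject must return weekly for repeat liver chemistries (ALT, AST, alkaline phosphatase, bilirubin").

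**Differential.** The instruction "Obtain complete blood count with differential to assess eosinophilia" appears only among the assessments that follow a liver stopping event.

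**The concern.** To put a subject in the continue-treatment branch, the investigator has to judge that no hypersensitivity symptoms are present. Of the three examples the protocol offers, fever and rash can be seen or reported. Eosinophilia can be known only from a laboratory result, and the central laboratory does not report that result during treatment. The one required differential comes after the decision it could inform. At stake is whether a subject with raised ALT and eosinophilia, but no fever, rash or liver symptoms, is dosed again because the investigator lacked a sign the protocol itself points to.

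**Working it through.** The plan states no figure on this point, so the check is a trace through the text plus some simple counts.

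1. **Who falls in the branch.** Appendix 13 gives an ALT upper limit of 48 U/L and a total bilirubin upper limit of 1.3 mg/dL. The band edges are 3 × 48 = 144, 5 × 48 = 240 and 8 × 48 = 384 U/L, with bilirubin below 2 × 1.3 = 2.6 mg/dL. The affected group has ALT 144 to <384 U/L and eosinophilia without another visible sign.

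2. **Whether the count can be recovered from reported values.** White cells minus neutrophils gives only the sum of lymphocytes, monocytes, basophils and eosinophils. All four are masked, so the eosinophil count cannot be worked out.

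3. **Whether another visible rule supplies it.** The branch lists four liver chemistries and no blood count. The LP flag (ALT ≥3×ULN) and the LR flag (ALT ≥5 to <8×ULN, bilirubin <2×ULN) in Appendix 13 direct review of ALT, or ALT and bilirubin, only. Appendix 13 also has a liver-event hematology panel that lists eosinophils, but the text does not say what triggers it or whether that result is masked.

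4. **When blood is already available.** In Table 6-1, on-treatment hematology after baseline falls at Weeks 4, 8 and then every 4 weeks to 56, which is 14 visits. Chemistry is drawn with it at Weeks 12, 24, 36 and 48. At those 4 visits an eosinophil result exists alongside the ALT that would raise the flag.

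5. **How long dosing can go on.** Dosing is every 4 weeks. Take ALT first raised at Week 12, and assume the Week 12 dose is given before the central result is back.
   - Upper band: the 2-week persistence rule acts at Week 14, before the next dose.
   - Lower band: the 4-week rule acts at Week 16, itself a dosing visit, so 0 or 1 further dose.
   - Step-down from upper to lower band, assuming the 4-week clock restarts: less than 2 + 4 = 6 weeks, which takes in the Week 16 dose only.

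   So about one further dose. Two would need step-down combined with ALT found between dosing visits.

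6. **What releasing eosinophils would reveal.** Appendix 13 range widths in thou/mcL are monocytes 1.10 − 0.20 = 0.90, basophils 0.20 − 0.00 = 0.20 and eosinophils 0.55 − 0.05 = 0.50. A lymphocyte count inferred from white cells minus neutrophils is now uncertain by 0.90 + 0.20 + 0.50 = 1.60. With the full eosinophil count released, it is uncertain by 0.90 + 0.20 = 1.10. That is still wider than the top of the adult CD19+ range, 660 per cmm = 0.66 thou/mcL. An above-range flag reveals less than the count. This is a rough bound: it assumes monocytes and basophils within range and does not address repeated counts in one subject.

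**The case against.** The strongest case against is that the gap may already be closed in material that was not available. Section 5.3 refers to the laboratory investigator manual for more on masked results. Figures 6-2 and 6-3, which chart this decision, are not shown. The liver-event panel may already be run and reported openly in this branch. That stands as a limit on certainty. It does not remove the point, because footnote a is unconditional as written and Section 6.3.1 sends the reader to Appendix 3 for the required actions.

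Investigators also have other protection. Section 6.3.10.1 allows for local tests, the medical monitor must be told within 24 hours, and the laboratory flags call for prompt clinic evaluation. Fever, rash, liver symptoms, ALT ≥8×ULN, bilirubin, INR if measured, persistence and inability to monitor all still trigger a stop. This stands too and makes the gap narrow, although none of these steps requires anyone to look at the eosinophil count.

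Finally, there is little left to protect in this study. Section 4.4.2 stops product when the sponsor terminates the study, SAP Section 4.2 records early termination, and the Amendment 7 rationale in Appendix 15 says assignments were unblinded. This is correct and largely sets the severity.

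**Conclusion.** The point holds in a narrow form. The visible text withholds one named example of a hypersensitivity sign at the moment the investigator decides whether to continue, for ALT ≥3 to <8×ULN with bilirubin <2×ULN. The cost is about one further dose, assuming 4-weekly dosing and no local differential. How often this would happen cannot be estimated from the documents. Severity is optional.

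Three stronger readings are tempting and are not supported:

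- A reader might infer that raised ALT with eosinophilia is a mandatory stop that masking defeats. Note 3 offers eosinophilia only as an example, sets no threshold, and leaves the judgement to the investigator. Seeing the count need not change the decision.
- A reader might count every remaining dose as exposure caused by the gap. Once ALT is below 3×ULN the symptomatic rule no longer applies, so later doses cannot be attributed to it.
- A reader might see a conflict with Section 5.3, whose visible list of masked results does not name eosinophils. That list is introduced as a partial one, so Table 6-5 can add to it without contradiction.

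**What to change.** Keep routine masking and add an exception to Table 6-5 footnote a:

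- When the LP or LR flag fires, the central laboratory also tells the investigator whether eosinophils from the same-visit hematology are above range. The sponsor sets the threshold; >0.55 thou/mcL, the upper limit in Appendix 13, is a usable default.
- Eosinophils from any liver-event hematology panel are reported unmasked.
- Lymphocytes, monocytes, basophils and B-cell values stay masked, and the stopping decision stays with the investigator.

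The cost is one conditional report flag and a short addition to the footnote, with no extra blood draw. The drawback is a little more information on the differential for the few subjects with ALT ≥3×ULN. The change also does not reach eosinophilia that first appears between visits with hematology; that still depends on the liver-event panel or a local test. If the laboratory manual or Figure 6-3 already provides for this, footnote a need only say so. The main beneficiaries would be any subject still dosed under this text and any later protocol that reuses it.
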